## 4.3 Exploratory

- Changes in cytokine concentration in nasal fluid and blood from baseline to 12 weeks of treatment.
- Mean change in migraine days from end of treatment (last month of 12 weeks of treatment) to follow-up.
- Mean change in migraine associated symptoms: nausea/vomiting, photophobia and sonophobia from baseline to 12 weeks of treatment.

#### 5 STUDY DESIGN

- This is a prospective, randomized, vehicle-controlled, double-blind, 3-arm parallel assignment study assessing the safety, tolerability, and efficacy of B244 delivered as an intranasal spray for preventive treatment in subjects with episodic migraine.
- This study will enroll 303 subjects.
- Enrolled subjects will undergo a 28 day baseline period to establish baseline headache frequency and characteristics.
- Subjects will be randomized at the end of the baseline period. Randomization will be 1:1:1 so that equal number of subjects will be treated in each Arm of the study.
- Subjects will be trained for in-home treatment/assessment on the use of the nasal spray, and apply their first dose of treatment under the supervision of study personnel on site. Subjects will remain under observation at the study site for 1 hour post dosing. Subjects will then be dispensed study medication for 12 weeks of at home dosing (either 1x10° cell/ml; 4x10° cells/ml; or vehicle). While at home, subjects will dose twice daily (am and pm) for 12 weeks during the prevention treatment phase. Subjects will be asked to visit the site every 4 weeks during the 12 week treatment period and 4 week follow-up.
- Daily assessments will be made during the 12 week double-blind treatment period for safety, tolerability and efficacy. Additional safety assessments will be made during the follow-up period 28 days after last treatment. Subjects will record their dosing, migraine incidence/severity/duration, and rescue (acute migraine specific) medications using a study diary.

#### **6 SELECTION OF STUDY PARTICIPANTS**

#### 6.1 Number of Participants Planned

Approximately 379 subjects will be consented and screened, allowing for a 20% screen fail rate. Approximately 303 subjects will be enrolled in order to achieve a target sample size of 264 (i.e., 88 subjects per arm), allowing for a 10-15% drop-out rate.

## **6.2** Study Population

Male and female subjects, 18 to 65 years of age, with a history of episodic migraine are eligible for enrollment. Subjects must be willing to refrain from using any treatments that are or might be considered useful for migraine prevention including recognized pharmaceutical products, investigational products, herbal medicines or supplements while participating in this study. Use of acute treatment is allowed throughout the study with the study subjects' usual acute medication of choice (usually a triptan, possibly NSAID or analgesic), but not intranasal formulations. Subjects should not initiate a preventive medication during study.

#### 6.3 Inclusion Criteria

Deviations from inclusion criteria are not allowed because they can potentially jeopardize the scientific integrity of the study, regulatory acceptability or participant safety. Therefore, adherence to the criteria as specified in the protocol is essential.

Participants eligible for enrollment in the study must meet all the following criteria:

- 1. Males and Females, 18 to 65 years of age.
- 2. In good general health as determined by a thorough medical history and physical examination, and vital signs.
- 3. At least a 1-year history of migraine with or without aura that began before the age of 50 years old and consistent with a diagnosis of migraine with or without aura according to the International Classification of Headache Disorders, 3rd edition, beta version.
- 4. Experiences 4-14 migraine days per month and 3-14 migraine attacks per month and no more than 14 headache days per month (including migraine and non-migraine headache days) in the 3 months prior to screening.
- 5. Experiences 4-14 migraine headache days per month during the baseline period.
- 6. Ability and willingness to abstain from taking medications not allowed by the protocol or administering any foreign substance intranasally.
- 7. Ability and willingness to complete a migraine-history diary from screening to treatment with study drug and a migraine-treatment diary from prevention treatment through the remainder of the follow-up period.

#### 6.4 Exclusion Criteria

Deviations from exclusion criteria are not allowed because they can potentially jeopardize the scientific integrity of the study, regulatory acceptability or participant safety. Therefore, adherence to the criteria as specified in the protocol is essential.

Participants will be excluded from the study if any of the following criteria are met:

- 1. Headache on greater than 14 days/month in any of the three months (90 days) preceding entry into the study.
- 2. Use of acute migraine-specific medications (e.g., ergotamine, triptan) on more than 10 days per month in the previous 3 months and during study.
- 3. Use of intranasal migraine medications during study.
- 4. Use of any intranasally administered over-the-counter product or nasal irrigation (e.g., neti pot) during study.
- 5. Opioids/barbiturates used on more than 4 days per month in the previous 3 months and throughout the duration of the study.
- 6. Use of analgesics (including acetaminophen, nonsteroidal anti-inflammatory drugs [NSAIDs], acetylsalicylic acid, or combination analgesics) for migraine or non-migraine headaches on more than 14 days per month in the previous 3 months and during study.
- 7. Use of migraine prevention medication within two months prior to study and throughout the duration of the study.
- 8. Botulinum toxin injection within 3 months prior to screening or during study.
- 9. Anti-CGRP monoclonal antibody (e.g., erenumab, fremanezumab, galcanezumab, and eptinezumab) injection or infusion within 4 months prior to screening or during study.
- 10. Small molecule anti-CGRP medications in the 30 days prior to the screening visit.
- 11. Use of systemic antibiotics during study.
- 12. Pregnancy or breast-feeding.
- 13. Female of childbearing potential not using adequate contraceptive measures.
- 14. Inability to give informed consent.
- 15. History of neurological, psychiatric, or any other medical condition that in the opinion of the investigator may compromise the subject's ability to safely participate in the study.
- 16. Subjects with any significant clinical abnormalities which may interfere with study participation.
- 17. Prior use of AO+ Mist
- 18. Subjects with immunodeficiencies, nasal lesions, nasal polyps, or sinus infections.
- 19. Subjects who have participated in an investigational drug trial in the 30 days prior to the screening visit.
- 20. Inability to maintain at least 80% diary compliance during the study from baseline to follow-up.

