## 7.3 Study Withdrawal and Withdrawal From Investigational Product and Stopping Criteria

A participant may withdraw from the study at any time at his/her own request, or may be withdrawn at any time at the discretion of the Investigator.

Reasons for withdrawal (participants who refuse to complete any remaining study visits) or discontinuation (participants who prematurely stop the application) at any time during the study may include, but are not limited, to the following:

For safety reasons, either at the discretion of the Investigator or at the participant's request

For protocol violations at the discretion of AOBiome

Due to concomitant therapy that could interfere with the results of the study (the Investigator will report all such information on the CRFs and decide, in accordance with AOBiome, whether the participant is to be withdrawn).

The reason for participant study withdrawal will be recorded in the electronic Case Report Form (eCRF). Data from participants withdrawing from the study will be considered evaluable up to the point at which they are withdrawn using the same criteria for evaluability as for participants who complete the study.

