#### **8.14 Rescue Medications**

Use of rescue medication is allowed throughout the study with subjects' usual acute migraine specific medication of choice to relieve their symptoms of an acute attack of migraine (usually a triptan, possibly NSAID or analgesic) and recorded in the eCRF. Subjects should avoid intranasal formulations of rescue medications. Subjects should not initiate a preventive medication during study and are prohibited from using any migraine-specific medications as preventive treatment between acute episodes. Subject may not start additional non-randomized medication and should immediately alert the study site PI. Subjects are encouraged not to start any new acute migraine/headache treatments during the course of the study and may be withdrawn from the study pending discussion with the PI and sponsor medical monitor in such cases. If discontinuation is necessary, this would be considered an early termination. A list of allowed rescue medications includes:

- All acute/abortive medications (excluding intranasal formulations) such as triptans (oral
  or injection route only) and ergot containing preparations (ergotamine tartrate, DHE 45
  by IM, SQ, IV) up to 10 days per month
- NSAIDs and analgesics (e.g., acetaminophen, acetylsalicylic acid, combination analgesics) for migraine and non-migraine headaches up to 14 days per month
- Opioid/barbiturate containing medications of up to 4 days per month

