## 14.5.1 Handling of Dropouts or Missing Data

Missing data will not be imputed for analysis.

Subjects who dropout after enrollment but prior to randomization will be replaced.

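### Section 6.4 makes on-study acute-medication use above a cap a ground for exclusion, while other sections treat it as eligibility, discretion, a usage limit or a deviation; if applied after randomisation, removal would depend on outcome

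*Protocol*

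**What the plan says.** Section 6.4 opens with "Participants will be excluded from the study if any of the following criteria are met" and adds "Deviations from exclusion criteria are not allowed because they can potentially jeopardize the scientific integrity of the study, regulatory acceptability or participant safety". Several listed criteria reach past randomisation:

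- No. 2 reads "Use of acute migraine-specific medications (e.g., ergotamine, triptan) on more than 10 days per month in the previous 3 months and during study".
- No. 5 reads "Opioids/barbiturates used on more than 4 days per month in the previous 3 months and throughout the duration of the study".
- No. 6 sets a 14-day monthly cap on analgesics over the same two periods.
- Nos. 3, 4, 7 and 11 (intranasal migraine drugs, other intranasal products, preventives, systemic antibiotics) also cover the study period. No. 20 (80% diary compliance) runs to follow-up.

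Other sections handle the same list or the same events differently:

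- The Clinical Trial Summary presents the list as conditions for enrolment. Section 7.2 has it reviewed at V1, V2 and V3.
- For concomitant therapy that could interfere with results, section 7.3 has the investigator "decide, in accordance with AOBiome, whether the participant is to be withdrawn". Section 12.5 repeats this.
- Section 8.14 says "Use of rescue medication is allowed throughout the study". Like 8.13, it sets monthly limits of 10, 14 and 4 days and gives no consequence for exceeding them.
- Section 14.6 summarises unmet criteria and non-permitted medication as deviations in all randomised patients.

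On data, section 7.3 keeps withdrawn participants evaluable up to withdrawal. Section 14.5.1 says "Missing data will not be imputed for analysis". Section 14.2 defines ITT as everyone randomised who received a dose.

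**The concern.** Two sites facing the same breach could act differently, and each could cite the protocol. One could withdraw the subject under 6.4; the other could record a deviation and carry on.

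The first course matters statistically because the trigger is close to the outcome. Section 11.10 counts a day of triptan use as a migraine day if the headache lasts at least 30 minutes, so passing 10 triptan days normally means more than 10 migraine days that month. Subjects may enter with up to 14 migraine days, so those who reach the cap on treatment are mostly those doing badly. Acute-medication days are also a secondary endpoint in their own right, and it would be cut off at the cap.

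If B244 reduces migraine days, more vehicle than active subjects would cross the cap. Losing them makes the vehicle arm look better than it is and shrinks the contrast on which the trial is sized. No. 11 (antibiotics) shares the drafting fault but is not tied to response.

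**Working it through.** **Planned figure.** Inputs from Statistical Considerations in the Clinical Trial Summary: mean changes −3.8 and −2.3 (difference 1.5 days), SD 4.0, one-sided 0.05 taken as stated, 80% power. n per arm = 2 × 4.0² × (1.645 + 0.842)² / 1.5² = 32 × 6.185 / 2.25 ≈ 88. Power at 88 is 80.0%. The plan's figure reproduces.

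**Assumptions not in the protocol.** Baseline mean 8 migraine days (SD 2.5–3 before truncation to the 4–14 entry range). A fixed share f of migraine days is treated with a capped drug. Baseline use is within the cap. A subject is removed if month-3 use exceeds the cap, and the month-3 change is analysed in those who remain.

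**Hand check.** Treat month-3 migraine days as normal with mean μ = 8 + change and SD 4. Removal starts above 10.5/f, so k = (10.5/f − μ)/4, the removed share is 1 − Φ(k), and the mean of those kept is μ − 4φ(k)/Φ(k). At f = 1:

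- Vehicle: μ = 5.7, k = 1.20, removed 11.5%, mean kept 5.7 − 4 × 0.194/0.885 = 4.82.
- Active: μ = 4.2, k = 1.575, removed 5.8%, mean kept 4.2 − 4 × 0.115/0.942 = 3.71.
- Difference 3.71 − 4.82 = −1.11 instead of −1.5. The same formula gives −1.34 at f = 0.8 and −1.49 at f = 0.6.

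**Simulation** (2 million per arm; slope of change on baseline 0 or −0.4, total SD 4.0). Power = Φ(d/SE − 1.645), with SE from the SDs and numbers kept out of 88 per arm.

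| Cap | f | Removed, vehicle | Removed, active | Effect (days) | Power |
|---|---|---|---|---|---|
| 10 days | 50% | ≤0.1% | about 0 | about 1.5 | 80% |
| 10 days | 70% | 2–4% | 1–2% | 1.36–1.40 | about 76% |
| 10 days | 85% | 7–9% | 3–4% | 1.23–1.26 | 70–72% |
| 10 days | 100% | 12–13% | 6–7% | 1.12–1.15 | 65–67% |
| 14 days | 85% | about 1% or less | about 0.5% or less | 1.43–1.47 | 78–79% |
| 14 days | 100% | 2–5% | 1–2% | 1.34–1.39 | 75–76% |

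With baseline mean 7–9 and f from 70% to 100% under the 10-day cap, the effect ranges over about 1.07–1.43 and power over 63–78%.

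**Second model** (removal if any of the three months exceeds the cap; counts floored at zero, so the full-data difference is below 1.5; baseline mean 8, average f 80%):

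- Removed: 10.2% on vehicle and 5.5% on active. The last-month difference goes from −1.29 to −1.07.
- If each subject's months up to and including the breach are averaged, the 12-week difference goes from −1.29 to −1.33, so it barely moves.
- With both arms at −2.3, removal is 10.3% and 10.2%, so no differential loss arises.

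**The case against.** The best defence is that 6.4 is an entry list with loose wording. The Summary and section 7.2 tie it to enrolment and randomisation, no section has it re-checked at V4 to V7, and sections 8.13, 8.14, 7.3 and 14.6 can be read as one process: a limit, a decision, a recorded deviation. Nos. 2, 5 and 6 also join the two periods with *and*, where nos. 8 and 9 use *or*, so read literally a subject under the cap before entry could never meet them later. This has weight, and a reader should not infer that the protocol plainly orders removal. It does not remove the conflict. Much of what nos. 3, 4 and 11 cover, and compliance to follow-up in no. 20, can only arise after V3. Section 11.10 also links diary compliance to remaining on the study.

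The size is open to challenge too. At 50% treated days, almost nothing happens. Section 8.14 expects some NSAID or analgesic users, who face the 14-day cap. Data collected before withdrawal stay evaluable, so a missing 12-week value is not certain. Removals might also come out of the drop-out allowance (303/3 = 101 per arm), which would give about 81% power at 70% treated. That leaves no room for ordinary drop-out and does not undo the bias in the estimate. The other points stand and limit the size.

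**Conclusion.** The conflict in the text stands. The bias is conditional: it needs sites to apply 6.4 after randomisation and the analysis to lose the later data. It then runs toward no effect, and only if B244 works. In the month-3 model, the planned 1.5 days becomes anything from about 1.5 (80% power) to about 1.1 (65–67% power), depending on the treated share, which the protocol does not give. The change is smaller under the 14-day cap and close to nil for a 12-week average that uses data up to the breach.

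Four stronger readings are not supported:

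- **Inflated type I error.** With equal arms, removal is balanced.
- **Site discretion decides who is in the ITT set.** Section 14.2 fixes membership; only the values available are at risk.
- **Automatic loss from the per-protocol set as a major violation.** Section 14.6 does not grade these deviations. A removed subject drops out of that set only by missing the Week 12 visit or if the breach is judged major.
- **Section 8.14 provides for withdrawal over the caps.** Its withdrawal clause concerns starting new acute treatments.

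This should be corrected because wording alone settles it.

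**What to change.** Reconcile the exclusion list in the Clinical Trial Summary with sections 6.4, 7.2, 7.3, 8.13, 8.14, 11.10 (diary compliance), 12.5 and 14.6, so that eligibility before randomisation is stated separately from conduct on study. The medication limits, and any decision to stop treatment, remain with the sponsor and are not prescribed here.

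For the analysis, state that exceeding a limit after randomisation is recorded as a protocol deviation. State also that it does not by itself end diary and visit data collection or remove observed values from the ITT analysis, whose membership section 14.2 already fixes.

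The cost is wording only, with no new assessments and no more patients. The downside is that the ITT estimate then includes subjects with heavier acute-medication use, which should be said when it is interpreted.

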## 7.2 Screening for Eligibility

Informed consent will be obtained prior to any screening assessments. Screening assessments (Visit 1; V1) will be performed within 2 weeks (-14 days) prior to the Baseline visit (V2) and will include: medical history and medication use, complete physical examination including height, weight, vital signs, and 12-lead ECG, a neurological examination, nasal inspection, laboratory testing, including blood sample for a comprehensive metabolic panel, complete blood count, chemistry, lipid panel, and liver function test, as well as urinalysis. Urine pregnancy test will be performed on WOCBP. All screening evaluations must be completed and reviewed to confirm that participants meet all eligibility criteria before entering baseline period on Day -28. Inclusion and exclusion criteria will be reviewed at Screening (V1), Baseline visit (V2), and Randomization visit (V3) to make sure nothing changed. Enrolled subjects will be asked to undergo a 4 week (Day -28 to 0) baseline period.

Eligible subjects will return to clinic on Day -28 (V2) for baseline assessments and will be sent home to record their migraine events and acute migraine medication use over the 28 day baseline period using a diary. Subjects will return to clinic on Day 0 (V3) for randomization upon confirming continued eligibility. Subjects are randomized at V3 upon confirming the inclusion/exclusion criteria and the entry criteria of 4-14 migraine headache days and 80% diary compliance during the baseline period.

For subjects who do not meet the 80% daily diary compliance but otherwise meet the 4-14 migraine days requirement during the baseline period, they can be provided additional opportunities to meet the 80% diary compliance requirement to enable continued eligibility for randomization. The following allowances can be made per investigator judgement on a case by case basis:

- If the anticipated diary compliance is slightly less than 80% or short by 4 daily diary entries by the day before the randomization visit, subjects can enter up to 4 additional days of diary entries (over the ±3 day visit window specified in the schedule of events in the protocol) as part of the baseline period and reschedule the randomization visit immediately after this period. This provides up to 7 additional days of diary entries to fulfill compliance. Twenty-eight days prior to the new randomization visit day can be re-evaluated for the baseline period.

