#### Migraine attack:

• An episode of any qualified migraine headache. To distinguish an attack of long duration from two attacks or to distinguish between attacks and relapses:

- o A migraine attack that is interrupted by sleep, or temporarily remits, and then recurs within 48 hours (i.e., <48 hours between the start of the migraine attack to the time of the recurrence) will be considered as one attack and not two.
- An attack treated successfully with medication but with relapse within 48 hours (i.e., <48 hours between the start of the migraine attack to the time of recurrence) will be considered as one attack.

Subjects will be advised to record their diary in the evening (after the night time dose) as a 24 hour reflective diary entry. For missed diary entries, subjects will be allowed to record up to 48 hours retrospective data. Subjects will be encouraged to record at least 80% of the daily diary days (80% diary compliance) during the study (from baseline to end of follow-up period) to remain on the study.

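### The 80% diary rule has three conflicting statuses, and exclusion no. 20 rests on diary days that do not exist when eligibility is reviewed

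*Protocol*

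**What the plan says.** The 80% threshold appears in three places with three different functions.

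- **Protocol 7.2 (entry gate).** Subjects are randomised at V3 on confirming the inclusion and exclusion criteria and "the entry criteria of 4-14 migraine headache days and 80% diary compliance during the baseline period". A subject who falls short may have the baseline extended, shifted or repeated. The same section states: "Inclusion and exclusion criteria will be reviewed at Screening (V1), Baseline visit (V2), and Randomization visit (V3) to make sure nothing changed".
- **Protocol 6.4 no. 20, and the synopsis (exclusion criterion).** The criterion is "Inability to maintain at least 80% diary compliance during the study from baseline to follow-up". The list in 6.4 opens with "Participants will be excluded from the study if any of the following criteria are met", and the section states: "Deviations from exclusion criteria are not allowed because they can potentially jeopardize the scientific integrity of the study".
- **Protocol 11.10 (encouragement and condition).** "Subjects will be encouraged to record at least 80% of the daily diary days (80% diary compliance) during the study", and the sentence continues "from baseline to end of follow-up period) to remain on the study". Missed entries may be filled in up to 48 hours back.

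Other sections bear on the consequences. The withdrawal reasons in 7.3 and 12.5 do not name diary compliance, but the lists are not exhaustive and include protocol violations at the sponsor's discretion. Under 7.3, data from withdrawn subjects stay evaluable up to withdrawal. Section 14.2 defines ITT with no diary condition and bars subjects with major protocol violations from the per-protocol (PP) set. Section 14.5.1 rules out imputation. Section 14.6 counts unmet eligibility criteria as a deviation.

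**The concern.** An eligibility criterion should be decidable when eligibility is decided. No. 20 covers a window that ends at Day 112, while the last review of criteria is at Day 0. Once a subject is randomised, the diary record can trigger no. 20 only by taking the subject off study or by marking the subject afterwards as wrongly enrolled.

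Diary completion after randomisation may depend on how the subject responds to or tolerates treatment. Removing subjects on that basis selects on a post-randomisation outcome. A subject removed during treatment supplies no later diary data, and nothing is imputed. A retrospective eligibility violation could also cost the subject a place in the PP set, on which efficacy is analysed alongside ITT. Sites that follow 6.4 strictly and sites that read 11.10 as encouragement could handle identical subjects differently.

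**Working it through.** **Inputs.** Baseline is 28 diary days (7.2: "the 28 day baseline period using a diary"). Treatment runs from Day 0 to 84 and follow-up from Day 84 to 112 (11.11), giving 84 and 28 days. The protocol derives no figure of its own from the rule, so there is none to reproduce. Neither 6.4 nor 11.10 says whether the 80% is one pooled percentage or a running one, so both are worked.

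**Thresholds.**
- Whole window: 28 + 84 + 28 = 140 days. 0.80 × 140 = 112 entries needed, so 28 may be missed.
- Baseline gate in 7.2: 0.80 × 28 = 22.4, so 23 of 28.

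**Pooled reading, full treatment diary (84/84).** Subjects randomised under 7.2 have 23 to 28 baseline entries.

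| Baseline entries | Fails no. 20 if follow-up entries are | Score at that limit |
|---|---|---|
| 23 | 4 or fewer | (23 + 84 + 4)/140 = 111/140 = 79.3% |
| 25 | 2 or fewer | (25 + 84 + 2)/140 = 111/140 = 79.3% |
| 27 | 0 | (27 + 84 + 0)/140 = 111/140 = 79.3% |
| 28 | cannot fail | (28 + 84 + 0)/140 = 112/140 = 80.0% |

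For the subject who entered with 23, failure is not certain until 24 follow-up days have been missed, because 28 − 24 = 4 is then the most that can still be recorded. All treatment data are in by that time.

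**Pooled reading, empty third month.** (28 + 56 + 0 + 28)/140 = 112/140 = 80.0%, a pass. This is the only passing combination. One further missed day gives 111/140 = 79.3%. If the ±3-day visit windows are assumed to make the third month and follow-up 25 to 31 days long, the best score with no third-month diary ranges from 77.9% to 82.1%.

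**Running reading (entries divided by days elapsed).**
- A subject who entered at 23/28 and misses the first treatment day, without filling it in within 48 hours, falls to 23/29 = 79.3%. If one treatment day is recorded before that miss, the score is 24/30 = 80.0% and the subject stays in. Two misses in the first six treatment days give 27/34 = 79.4%. A subject admitted properly under 7.2 therefore has very little slack early in treatment.
- The subject with an otherwise complete diary and an empty third month drops below 80% on day 22 of that month: 84/106 = 79.2%.

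**Window against endpoint.** Follow-up supplies 28/140 = 20% of the pooled days. Among the listed efficacy endpoints, follow-up diary days feed only the exploratory change in migraine days from end of treatment to follow-up. The secondary diary endpoints use baseline and treatment days.

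**The case against.** The strongest defence is that no. 20 is a judgement of capacity at entry. It is worded as an inability and mirrors inclusion no. 7, which asks for ability and willingness to keep the diary through follow-up. Criteria are reviewed only up to V3, 7.2 supplies the measurable test, and diary compliance is not a named withdrawal reason. This reading is possible, but the text does not settle it. No. 20 sets a numerical threshold over a window reaching follow-up, 6.4 allows no deviation, and 11.10 ties the same threshold over the same window to staying in the study.

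Three stronger conclusions might be inferred, and the protocol does not support them.

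- **That the rule generally removes complete treatment diaries and keeps empty third months.** It does not. The first needs one to five baseline misses plus a nearly empty follow-up diary. The second needs every other day recorded. Most subjects who skip the third month would fail. Both cases also assume the pooled reading, which is natural but unstated; the word maintain also fits a running percentage.
- **That the ITT sets would differ between sites.** ITT has no diary condition, and data up to withdrawal are kept. A subject failing late in follow-up loses no 12-week efficacy data. An effect on PP is possible but depends on what counts as a major violation, which a SAP may define.
- **That a power loss can be stated.** The protocol gives no rate of on-study diary non-compliance, and some removals could fall within the 10–15% drop-out allowance.

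**Conclusion.** The point stands as a contradiction with a practical consequence. Sections 7.2, 6.4 no. 20 (with the synopsis) and 11.10 give one rule three statuses and must be reconciled. As written, randomised subjects can be taken off study, or marked afterwards as ineligible, for diary behaviour after randomisation. What is at risk is data after removal, and possibly PP membership; ITT membership is not.

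The number of subjects affected cannot be sized from the document. The day counts rest on nominal 28, 84 and 28-day periods and show only what the rule can do: fail a full treatment diary at 79.3%, pass an empty third month at exactly 80.0%, or, on a running reading, fail a validly enrolled subject on the first treatment day. The contradiction does not depend on which reading is meant.

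**What to change.** Limit exclusion no. 20, in 6.4 and the synopsis, to less than 80% diary compliance in the 28-day baseline period, including any baseline extended, reset or repeated under 7.2. In 11.10, delete the closing words that make 80% a condition of staying in. State there that compliance below 80% after randomisation is recorded as a deviation and is not by itself a ground for removal from the study or from ITT.

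The cost is a wording change in three places, with no effect on visits, treatment or sample size. The downside is that some subjects with sparse diaries stay in follow-up and add a little noise.
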